Aim #3: To determine if active TENS alters pain processing in women with fibromyalgia and if improvement in clinical symptoms correlates with normalization of pain processing physiology. We will evaluate change in these physiologic parameters in responders versus non-responders as assessed clinically.

Aim #4: To determine if PROMIS is a useful instrument for assessing outcome for fibromyalgia by comparing to the revised version of the fibromyalgia impact questionnaire (FIQ-R).

Healthy Control Aims:

Aims:

Physically active women with fibromyalgia will have a similar phenotype (pain thresholds and conditioned pain modulation) and cytokine profile to physical active women without pain; conversely sedentary women with fibromyalgia will have a similar phenotype and cytokine release profile to sedentary women without pain.

Aim #5 will perform quantitative sensory testing to profile excitability and central inhibition in individuals with fibromyalgia and healthy controls; both sedentary and physically active individuals will be recruited in each cohort.

Aim #6 will examine for cytokine release profiles in immune cells (monocytes) from the sedentary and physically active individuals with and without fibromyalgia.

Study Synopsis

Protocol Title	Fibromyalgia Activity Study with TENS (Transcutaneous Electrical Nerve Stimulation)
Protocol Number	
Name of Sponsor	Funded by NIH NIAMS Performed at University of Iowa, Vanderbilt University
Investigational Product	TENS (Transcutaneous Electrical Nerve Stimulation) TENS is a non-pharmacological agent which delivers electrical stimulation by a battery operated device via electrodes placed on the skin. TENS is considered to be a safe, inexpensive and non-invasive modality used to treat a variety of acute and chronic pain conditions.
Phase of Development	Phase II Clinical Trial
Purpose of Study	The primary aim of the study is to test the effect of the long-term use of TENS on movement-related pain as measured by a numeric rating scale (NRS) during six minute walk test (6MWT) in women with fibromyalgia with random assignment to three treatments: standard care (No TENS), placebo TENS and active TENS.
Indication	Women with Fibromyalgia, ages 18-70
Number of Centers	The study will be conducted at 2 study sites: University of Iowa and the Vanderbilt University
Study Duration	5 years

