Exclusion Criteria	
 • Current or history of cardiovascular, pulmonary, neurological, endocrine, or renal disease that would preclude the involvement in the study. • TENS use in the last 5 years • Pacemaker • Uncontrolled blood pressure or diabetes • Neuropathic pain condition • Systemic autoimmune disorder (Lupus, PMR, RA, Psoriatic arthritis) • Spinal fusion – cervical or lumbar • Metal implants in the spine • Severe skin allergy to adhesive • Allergy to nickel • Pain less than 4 • Pregnancy • Epilepsy • Change in or new drug or treatment program within the last month or in the next 2months, i.e. must have a stable treatment plan • Unstable medical or psychiatric condition which in the opinion of the investigator could compromise the subject’s welfare or confound the study results
Planned Sample Size	Final sample size of 264 subjects divided into 88 subjects per group. We will recruit 316 subjects based on a 20% projected attrition.
Randomization	Patients will be randomly allocated on the second visit after a re-assessment of eligibility. We will use a permuted block schedule, stratified by site. The randomization schedule will be implemented using SAS v9.2 PROC PLAN, creating blocks of size 6 for each of the strata factors.
Study Device Dosage and Administration	
FDA Summary of Empi Select TENS Unit: TENS is a non-pharmacological agent which delivers electrical stimulation by a battery operated device via electrodes placed on the skin. TENS is considered to be a safe, inexpensive and non-invasive modality used to treat a variety of acute and chronic pain conditions.
 
510(k) Summary for 300 PV Complete Electrotherapy Systems 1. Manufacturer Empi [name]

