Criteria for Evaluation	
Primary Efficacy Endpoint:
 
 • Pain with movement (NRS) during 6MWT 
Secondary Efficacy Endpoints:
 
 • Health History/Demographics • Vital Signs • Confirmation of ACR 1990 Criteria for FM/Tender Point Exam • 2010 ACR Criteria • NRS Rest Pain, Rest Fatigue, Movement Pain, Movement Fatigue • BPI • PROMIS • FIQR • SF-36 • MAF • TSK • IPAQ • PSQI • PSEQ • PCS • Global Impression of Change • Accelerometry • 6MWT • STS • FR • PPT • CPM • TENS • Blinding
Statistical Methods	
 • Continuous variables will be summarized with descriptive statistics (n, mean, standard deviation, standard error, median, first and third quartiles, and minimum and maximum). • Categorical variables will be described with counts and percentages. The endpoints (VAS, BPI, PPT, CPM, and 6MWT, STS, FR and accelerometry measures) will be treated as continuous variables as well as scores from questionnaires (FIQR, SF-36, MAF, and TSK, PROMIS). • Changes from initial measurement to one month after randomization will be calculated for each of these endpoints. Changes in outcomes and percent changes in outcomes will be treated as continuous variables and will be summarized with descriptive statistics. Outcomes will be summarized by visit, as change from initial measurement, and percent

	
change from initial measurement. Continuous endpoints may also be categorized into discrete variables when appropriate. Shift tables may be utilized to investigate shifts in outcome categories from baseline to one month after randomization. SAS v9.2 or higher will be used for all analyses and a significance level of 0.05 will be used for all statistical tests. In the case that endpoints are found to be non-normal, appropriate transformations will be employed and non-parametric tests may be used

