
(ref2) Carpenter J and Kenward MG (2013) Multiple Imputation and its Application. John Wiley & Sons Ltd, West Sussex, England.

Aim #2: The primary endpoint of Aim #2 is the change (visit 3 – visit 1) in fear of movement scores. Secondary endpoints for this aim include changes in function, fatigue, resting pain, function, use of rescue analgesic medications, and quality of life. Additionally physical function measures will be determined using accelerometer data and data obtained during a course of specific functional tasks. Rescue analgesic medications will be recorded as number and dose of medications, indicators for increases or decreases in frequency or dose, and any utilization. Comparisons between the randomized groups for these outcomes will be performed as described in Aim 1. Additional analyses, using the change in fatigue, fear of movement, function, quality of life and resting pain measures as dependent variables in linear regression models, associations between these outcomes and changes in pain values will be investigated.

Aim #3: The primary endpoints of Aim #3 are the change (visit 3 – visit 2) in PPT and DNIC/CPM for those who complete one month of active TENS. After one month of active TENS, participants will be clinically evaluated and classified as responders or non-responders using recently published criteria for fibromyalgia subjects [7]. Comparisons of these physiologic parameters will be made in responders versus non-responders as described in Aim 1. Since responder status is not randomized, it is expected that that the linear mixed model will also include covariates such as change in opioid status, medication intake, and TENS use. Multiple variable logistic regression (with associated odds ratio estimates and ROC curves) will also be utilized to investigate factors related to being a responder or not.

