Aim #3	V3-V2	Change in PPT, CPM for those who complete one month of active TENS.	
 • Classification of participants who complete one month of active TENS as responders or non-responders using published criteria⁵⁰ • Linear regression models will assess for factors that predict responders and non-responders to treatment using data obtained prior to the intervention.
Aim #4	V2 V3 V4	Prior to randomization: FIQR and SF-36. PROMIS modules for comparison to FIQR and SF-36.	
 • Pearson correlation and testing for nonzero correlation between PROMIS modules (and corresponding domains of the FIQR and SF-36. • Multiple linear regression may also be used to investigate this relationship while controlling for potential confounding variables. • FIQR, PROMIS and SF-36 will be obtained at 3 time points and summarizes as values, changes from pre-treatment and percent changes, changes observed in the randomized phase. Time points are (1) V2: pre-treatment; (2) V3 randomized phase and (3) V4 non-randomized active TENS. • Linear models may be used where treatment status ((1) V2: pre-treatment; (2) V3: randomized phase and (3) V4: non-randomized active TENS) is treated as a time-varying covariate to estimate the impact of changes in treatment status.
Exploratory Analysis		Changes in pain Responder status Relationships between endpoints Relationships between changes in pain, sensory and quality of life measures	
 • Further investigation during non-randomized phase, two months of active TENS (initially randomized to active TENS and those with a single month of active TENS (initially randomized to placebo TENS or standard care) • Multivariate methods (e.g. partial least squares and principal component analysis and classification and regression trees.

--	--	--	--

Table 3: List of equipment, form per test and measure

Area	Form	Visit	Equipment: Clipboards, Pens, Computer/Form
	Screening Log	Pre Visit	Computer/Form
Surveys	Consent	1	Computer/Form
	Health History/Demographic	1	Computer/Form
	Diagnostic Confirmation	1	Computer/Form
	Eligibility Confirmation	1, 2	Computer/Form
	FIQR	1,2,3,4	Computer/Form
	MAF	2,3,4	Computer/Form
	TSK	2,3,4	Computer/Form
	Medication	1,2,3,4	Computer/Form
	SF-36	2,3,4	Computer/Form
	PROMIS	2,3,4	Computer/Form
	IPAQ	2	Computer/Form
	PSQLI	2	Computer/Form
	PSEQ	2	Computer/Form
	PCS	2	Computer/Form
	Blinding Question Researcher and Subject	3	Computer/Form

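### Aim #3 asks about a correlation between clinical improvement and pain physiology, but its only committed tests reduce improvement to responder or non-responder; a pre-specified continuous model beside them would be a cheap gain.

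*Combined protocol and SAP*

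**What the plan says.** The Aims section and the Objectives in the Study Synopsis state Aim #3 in two sentences. The first asks whether active TENS alters pain processing and "if improvement in clinical symptoms correlates with normalization of pain processing physiology". The second says how: "We will evaluate change in these physiologic parameters in responders versus non-responders as assessed clinically".

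The Study Synopsis (Statistical Methods Aim #1-#4, Aim #3) fixes endpoints and population: "The primary endpoints of Aim #3 are the change (visit 3 – visit 2) in PPT and DNIC/CPM for those who complete one month of active" treatment. These women are classified by published fibromyalgia criteria, cited but not reproduced, and then "Comparisons of these physiologic parameters will be made in responders versus non-responders as described in Aim 1". Because responder status is not randomised, the mixed model is expected to include change in opioid status, medication intake and TENS use. Logistic regression with ROC curves is added for factors related to responder status.

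The Aim #3 row of the Data Analysis Plan table has two entries: "Classification of participants who complete one month of active TENS as responders or non-responders using published criteria", and regression models predicting that status from data obtained before the intervention.

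Two other places touch on continuous relationships. The Aim #2 regressions on change in pain take fatigue, fear of movement, function, quality of life and resting pain as dependent variables; PPT and CPM are not among them. The exploratory paragraph after Aim #4, and the Exploratory Analysis row of the table, mention relationships between changes in pain, sensory and quality-of-life measures, with multivariate methods and trees as optional tools.

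**The concern.** Both sides of the Aim #3 question are available on graded scales. Movement pain and FIQR are scored at visits 2 and 3, as are PPT and CPM, and the synopsis treats changes in outcomes as continuous. A responder split discards the grading on the clinical side: a woman just past the threshold counts the same as one with complete relief, and two women just either side of it count as opposites. A difference in means between two classes therefore answers a question about correlation only in part, and usually with less power.

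What is at stake is the link between symptom relief and physiology in the trial's hypothesis. If the responder comparison were null, a reader could not easily tell an absent link from one blurred by the split. No other committed analysis would help to separate the two.

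**Working it through.** **Inputs from the documents.** Significance level: "a significance level of 0.05 will be used for all statistical tests" (sidedness not stated; two-sided assumed). Size: "Final sample size of 264 subjects divided into 88 subjects per group", with 316 recruited and 20% attrition projected. No power, effect size, correlation or responder share is given for Aim #3, so there is no stated figure to reproduce.

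**Number available.** Aim #3 uses the active arm. From the recruitment figures, 316 × 0.8 / 3 = 84.3, so about 84. The stated final size is 88; losing 10% of those gives 79. All three are carried below.

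**Assumptions.** Change in clinical score and change in PPT (or CPM) are bivariate normal with correlation r. The responder criterion acts like a threshold on that one clinical score. The share of responders is p. Covariates, and the presence of two endpoints, are ignored.

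**Step 1: information kept.** The fraction kept is RE = φ(z_p)² / [p(1 − p)], where φ is the standard normal density at the cut.

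| p | φ(z_p) | RE | Information lost |
|---|---|---|---|
| 0.50 | 0.399 | 0.159/0.25 = 0.637 | 36.3% |
| 0.40 | 0.386 | 0.149/0.24 = 0.622 | 37.8% |
| 0.30 | 0.348 | 0.121/0.21 = 0.576 | 42.4% |

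Outside that range the loss is larger: 51.0% at p = 0.20 and 65.8% at p = 0.10.

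**Step 2: power.** The split attenuates the correlation to r√RE. By Fisher's z, power = Φ[atanh(r)·√(n − 3) − 1.96], with r replaced by r√RE after the split.

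For n = 84 and r = 0.30, √(n − 3) = 9:
- Continuous: 0.3095 × 9 − 1.96 = 0.826, power 80%.
- p = 0.50: r√RE = 0.239, atanh = 0.244; 0.244 × 9 − 1.96 = 0.237, power 59%.
- p = 0.30: r√RE = 0.228, atanh = 0.232; 0.232 × 9 − 1.96 = 0.125, power 55%.

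Simulation at a 35% responder share gave 80% against 57%.

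**Step 3: sensitivity.**

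| n | r | Continuous | Split, p = 0.30 to 0.50 |
|---|---|---|---|
| 84 | 0.20 | 45% | 28-30% |
| 84 | 0.30 | 80% | 55-59% |
| 84 | 0.40 | 97% | 81-85% |
| 79 | 0.30 | 77% | 52-57% |
| 88 | 0.30 | 81% | 57-61% |

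The assumed correlation matters far more than the choice among 79, 84 and 88. In simulation at n = 88 and r = 0.50, both tests are nearly certain to detect the link: over 99% against 97-98%.

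**Step 4: a composite criterion.** Suppose a responder must pass on two domains, each correlated 0.30 with physiology and 0.3 to 0.7 with each other, with 22% to 58% responding and n = 84. Simulated power is about 59-71% for the responder class, 79-81% for continuous change in pain alone, and 86-94% for the continuous average of both domains. Under this model the gap to pain alone narrows but does not close. Had physiology tracked mainly a non-pain domain, the composite class could beat pain alone.

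**The case against.** The strongest reply is that the responder comparison is what the aim itself announces. A reader might infer that the analysis contradicts the aim. It does not: the synopsis implements the aim's second sentence, and the general methods allow continuous endpoints to be categorised where appropriate. What remains is that the first sentence poses a correlation, which a two-class comparison answers only in part. For Aim #4, by contrast, the plan commits to Pearson coefficients.

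A reader might also infer that no continuous look is planned. That is too strong. The exploratory text foresees relationships between pain and sensory changes, and its optional wording may qualify only the choice of method. Still, it names no model, estimate or test, so it gives partial cover.

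Third, replacing the responder class with movement pain alone could cost power. The aim speaks of clinical symptoms. If movement pain is only a proxy for overall improvement, with correlation ρ, it keeps ρ² of the information. It then beats a 30-50% split only if ρ exceeds √0.576 = 0.76 to √0.637 = 0.80. The documents give no such correlation. This stands, and it is why the continuous model should be added rather than substituted, with a second clinical measure.

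Finally, not all mechanistic evidence rests on this test. Whether active TENS alters pain processing is a separate part of Aim #3, and PPT and CPM are secondary efficacy endpoints. The primary endpoint is unaffected.

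**Conclusion.** The point holds as a cheap improvement. Every committed Aim #3 analysis uses binary responder status, and none relates the amount of improvement to the amount of change in PPT or CPM. The planned test is valid, but it probably wastes information and only partly matches its question.

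A reader might take a 36-42% loss, or a fall from 80% to 55-59% power, as properties of this trial. The documents do not support that. Those figures rest on an assumed r of 0.30, an assumed responder share of 30-50%, two-sided testing, normality, and a criterion that behaves like a cut of one score. With r = 0.40 the split still leaves 81-85% power; with r = 0.20 neither test is adequate. A responder share of 10-20% would make the loss larger. A criterion built on several domains could move it either way.

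**What to change.** In the Aim #3 text of the Study Synopsis and the Aim #3 row of the Data Analysis Plan table, keep the responder comparison and pre-specify beside it:

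- a linear model of visit 3 minus visit 2 change in PPT, and another for CPM, on continuous change in movement pain over the same interval;
- the same models with change in FIQR as the second clinical measure;
- adjustment for baseline PPT or CPM, the baseline clinical score, and the covariates the synopsis already expects (change in opioid status, medication intake, TENS use);
- the slope with its 95% confidence interval as the reported result.

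The cost is a few lines of text and a few extra models, with no new visits or measurements, since Table 1 schedules all these measures at visits 2 and 3. The downside is that each continuous score covers only part of a possibly composite criterion, which is why the responder comparison stays.

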
Statistical Methods Aim #1- #4
	
Aim #1: The primary endpoint of Aim #1 is the change (visit 3- visit 2) in pain scores during movement. In order to evaluate the effectiveness of long-term use of TENS (Aim 1), the primary analysis will be the comparison of change in pain (with movement for those randomized to either active TENS, placebo TENS, or standard of care). The comparison of the change (visit 3 – visit 2) in pain for the three groups will be made using linear mixed model analysis for repeated measures with treatment group, time (visit2 and visit3), and treatment group*time interaction as the fixed effects. The test for the treatment group*time interaction effect corresponds to the test comparing mean change among the groups. Post-hoc pairwise comparison of mean change between groups will performed by test of mean contrasts estimated from the fitted linear mixed model with p-values adjusted using Bonferonni’s method to account for the number of tests performed (i.e. 3 tests for all pairwise comparisons). It is expected that the randomization will lessen the need for covariate-adjusted analyses. However, in the event that adjusted analyses are necessary, a secondary comparison of the change in endpoints for the three groups will be made by expanding the linear mixed model to include covariates. Potential confounders include age, race, ethnicity, educational attainment, marital status, TENS dose/intensity, change in opioid status, medication intake and use of rescue medications.
 
While every effort will be made to follow-up with patients, preliminary data suggests that approximately 10% of the patients will not return for follow-up. The ITT analysis will be performed using all available data for all randomized participants. In the presence of missing data, under the assumption of missing at random (MAR), linear mixed model analysis which can handle incompletely observed subjects and uses a likelihood estimation method will provide correct likelihoods and lead to valid estimates (ref1). However, since the data under analysis cannot distinguish if data is MAR or it is missing not at random (MNAR), sensitivity analysis will also be performed using pattern mixture models. Multiple imputations will be used for sensitivity analysis by imputing from a non-random pattern mixture model (ref2).
 
Furthermore, based on previous work, it is expected that approximately 5% of subjects randomized to active TENS may not receive a full dose of active TENS because they did not achieve the adequate intensity dose. In the primary ITT analysis, these patients will be included as randomized. However, as an additional analysis a modified ITT (mITT) analysis will be conducted. This analysis will utilize an ITT principle in terms of randomization but will be limited to those who achieved at least one adequate intensity dose.
 
(ref1) Molenberghs G. and Kenward MG (2007) Missing Data in Clinical Studies. John Wiley & Sons Ltd, West Sussex, England.

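### Aim #3 does not say how its covariates enter the two-visit mixed model; as main effects, change in opioid status and TENS use cannot adjust the responder*time test

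*Combined protocol and SAP*

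**What the plan says.** The Aim #3 text in the Study Synopsis (Statistical Methods Aim #1-#4) sets the outcome: "The primary endpoints of Aim #3 are the change (visit 3 – visit 2) in PPT and DNIC/CPM". The analysis is restricted to women who finish the month on the active device. It takes its method from the first aim: "Comparisons of these physiologic parameters will be made in responders versus non-responders as described in Aim 1". It then notes that responder status is not randomised and expects that the "linear mixed model will also include covariates such as change in opioid status, medication intake, and TENS use".

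The Aim #1 text defines the model being borrowed, with "treatment group, time (visit2 and visit3), and treatment group*time interaction as the fixed effects". It identifies the test of interest: "The test for the treatment group*time interaction effect corresponds to the test comparing mean change among the groups". An adjusted comparison "will be made by expanding the linear mixed model to include covariates", with no further detail on how they enter.

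No covariate*time term appears anywhere in the document. The only covariate described as time-varying is treatment status, under Aim #4. The Aim #3 row of the Data Analysis Plan table contains no adjusted mixed model; it lists regression models for predictors of response, which answer a different question.

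**The concern.** Heavier TENS use, or a change in opioids, could plausibly drive both clinical response and the change in PPT or CPM. That is the reason for having these covariates in a comparison of self-selected groups. But the tested term is a within-woman contrast between two visits. A covariate that takes the same value at both visits, with a single coefficient, raises or lowers both of her measurements equally and says nothing about her change.

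An analyst who adds the named covariates in the usual way would therefore see coefficients for opioid change and TENS use in the output, call the responder*time result adjusted for them, and report a figure identical to the crude one. A link between response and physiology that came only from TENS use would then appear to have survived adjustment for TENS use.

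**Working it through.** **Inputs from the document.** Outcome: visit 3 minus visit 2 change. Model: group, time, group*time. Population: completers of a month of active TENS. Arm size: 264/3 = 88. Significance level: 0.05. Expected non-return: about 10%. The plan gives no effect size, power, responder rate or correlation for Aim #3, so all of those below are assumptions.

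**1. Algebra.** For woman i let R be responder status and C a covariate with one value per woman:

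- Visit 2: Y2 = a + bR + gC + u + e2
- Visit 3: Y3 = a + bR + t + dR + gC + u + e3
- Change: Y3 − Y2 = t + dR + (e3 − e2)

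The term gC has gone, and d is the responder*time effect. Three other codings keep the covariate in the change:

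- With a C*time term (coefficient h): change = t + dR + hC + error.
- With visit-specific values M2 and M3: change = t + dR + g(M3 − M2) + error.
- With TENS use coded 0 at visit 2: change = t + dR + gC + error.

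**2. Numerical check.** REML fits to one simulated data set of 88 women (26 responders, 62 non-responders; assumed coefficients). Only whether the estimate moves is informative, not its size. Figures are for compound symmetry unless stated.

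| Model, complete pairs | responder*time | SE | t |
|---|---|---|---|
| No covariates | 0.3292 | 0.2769 | 1.189 |
| Opioid change, TENS use, medication as one-value main effects | 0.3292 | 0.2769 | 1.189 |
| As above, but medication visit-specific | 0.4281 | 0.2780 | 1.540 |
| Opioid change and TENS use coded 0 at visit 2, medication visit-specific | 0.1622 | 0.2769 | 0.586 |
| One-value covariates, each with covariate*time | −0.0440 | 0.2825 | −0.156 |

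The two-sample t-test on change gives 0.3292/0.2769 = 1.189, which confirms the plan's own statement that group*time tests mean change. An unstructured covariance gives the same values in rows 1, 2 and 5, and 0.4289 and 0.1582 in rows 3 and 4.

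**3. Incomplete pairs.** With about 10% of visit 3 values removed (9 of 88), one-value main effects move the estimate from 0.336 to 0.316 (compound symmetry) or from 0.337 to 0.320 (unstructured). Covariate*time terms move it to −0.079 and −0.077.

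**4. Possible size.** Assume 88 women, 40% responders, and TENS use correlated r with both latent improvement and the change in PPT or CPM, with no other link between them. 4000 replicates per row:

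| Assumed r | Rejection, one-value main effect |
|---|---|
| 0.2 | 6.4% |
| 0.3 | 10.1% |
| 0.4 | 21.8% |
| 0.5 | 45.5% |

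Regressing the change on responder status plus TENS use gives 4.7% to 5.4%. Results are similar with 30% or 50% responders.

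The last row can be checked by hand. The correlation induced between responder status and change is r² × φ(z)/√(p(1−p)). With p = 0.4, z = 0.253 and φ(z) = 0.386, this is 0.25 × 0.386/0.490 = 0.197. The noncentrality is 0.197 × √88/√(1 − 0.197²) = 1.89. Against a critical value of 1.99 on 86 degrees of freedom, rejection is about 46%.

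**5. All three covariates together.** In 2000 further data sets with assumed confounding through opioid change, TENS use and medication, and no true responder effect, the unadjusted comparison (equal to the one-value main-effect model) rejected in 16.1%. Adjusting only for change in medication rejected in 24.0%. Adjusting the change for all three rejected in 5.7%.

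**The case against.** The strongest reply is that the plan never fixes the coding. It does not say main effects only, nor one value per woman. A medication log is listed in all four sessions of the Order of Testing table, so visit-specific medication values are available. Home TENS starts at visit 2, and TENS use in the last 5 years is an exclusion, so coding TENS use as 0 at visit 2 is natural. With that coding, a rerun of step 4 (1500 replicates, unstructured covariance) rejected in 5.7%, 5.5% and 4.8% at r = 0.3, 0.4 and 0.5, against 10.3%, 22.2% and 46.9% with the one-value main effect.

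This stands. A reader might infer from the algebra that the adjusted Aim #3 comparison simply is the unadjusted one. The document does not support that, because it permits codings that do adjust, and exact equality needs complete pairs. It does not remove the point, however: change in opioid status is one value per woman by definition, no interaction with time is mentioned, and time-varying covariates are named only under Aim #4.

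Three further replies have some force. Eligibility requires a stable treatment regimen, past and projected, which limits opioid and medication change by design, so the covariates are not the only safeguard. Aim #3 asks whether improvement correlates with physiology, so the crude association is of interest in itself; that argues for reporting both figures, not for an adjustment of unknown effect. And Aim #3 is mechanistic, with no bearing on the randomised movement-pain comparison.

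**Conclusion.** The point holds as a specification gap with a definite consequence. Whether the Aim #3 adjustment for opioid change and TENS use does anything depends on a coding choice that the plan leaves open, and under the ordinary choice it does nothing with complete pairs and almost nothing with about 10% of visit 3 values missing. That part is algebra and rests on no assumed correlation.

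The size of any harm is not known. A reader might take 46% as the false-positive rate of Aim #3. It is not: it needs a correlation of 0.5 on both paths, and at 0.2 the rate is about 6%. The documents give no correlation and no responder rate, and no separate figure was derived for opioid change. Visit-specific medication values would move the test but would not deal with confounding through the other two covariates. This is a cheap improvement to a secondary aim; the primary efficacy analysis is untouched.

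**What to change.** State the following in the Aim #3 analysis text, and carry it into the Aim #3 row of the Data Analysis Plan table:

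- Each covariate with one value per woman (change in opioid status, TENS use over the month) enters with its covariate*time interaction. Equivalently, the visit 3 minus visit 2 change in PPT and in CPM is regressed on responder status plus these covariates.
- Medication intake enters the mixed model as visit-specific values, or enters the regression of change as its own change.
- Crude and adjusted responder differences are reported side by side.

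The cost is a few sentences and no new data: medication logs and TENS device data are already collected. The statistical price is a few model degrees of freedom and possibly a slightly wider interval for the responder difference where covariates correlate with response. In the complete-pair example the standard error went from 0.277 to 0.283.
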